### STEP 2:

**Primary goal:** Measure the time spent alive and non-delirious in the ICU up to 14 days from randomization with EyeControl-based communication compared with the standard of care, in a randomized-controlled fashion.

#### Secondary goals:

1. Assess the safety, tolerability, and ease of use of the EyeControl device; Specifically, we will assess on a daily basis for any adverse events related to the device. We will also document need for re-training on the device as a marker for ease of use.
2. Measure the length and intensity of use for communication and call for help; Intensity will be measured by the number of times the device is used and for which purpose as a categorical measure (eg, call for help, talk using predefined sentences, communicate using letter by letter dictation etc).
3. Correlate between the monitoring data and clinical data: the device will assess CAM-ICU independently, and a study team member will repeat this analysis and the documented results will be documented. We will also track any clinical decision making based on wakefulness time information (for example a decision to add melatonin agonist to promote sleep) ;
4. Measure the cognitive and functional long-term outcomes, by phone questioners, to be done in a blinded fashion at 6 months from ICU discharge.

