As part of its operation, the device captures photographs and video of the patient's eyes (figure 3). In addressing the secondary goal of potential correlation between eye behavior and clinical events, we will explore this possibility by evaluating photographs of the eyes at the times of clinical events (i.e. hypoxia, new onset shock, or new onset sepsis). The device will activate the image data collection only after 50 consecutive frames of eye-in-the-image. This should be a safety index to verify that the device is only recording the eye. It will stop recording immediately when non-eye-in-the-image occurs. Data processing to decide if an eye is in the image is done locally on the device, so eventually only images of eyes should be collected. All external image data processing will be done following deidentification of the data, using the patient code only as an identifier.

Figure 3. Example photographs captured by the EyeControl device.

No randomization or blinding is planned for this step of the study, and no samples are planned to be collected.

---

**STEP 2: MEASURE REDUCTION IN DELIRIUM-FREE AND ALIVE DAYS IN THE ICU WITH EYECONTROL-BASED COMMUNICATION COMPARED WITH THE STANDARD OF CARE.**

The second step will be similar to the operation of the first one, in terms of patient screening and enrolling. The main difference will be the randomization process. Patients will be randomized to use EyeControl for as much as they wish, versus the standard of care. Randomization will be done centrally, and will be stratified to the specific unit, gender and age, race and ethnicity.

The primary goal of the second step will be to measure the time spent alive and non-delirious in the ICU with EyeControl-based communication compared with the standard of care. Delirium will be defined as CAM-ICU positive, starting at day 1 of use (following the day of training), up to 14 days from randomization or ICU discharge, the earliest. However, patients could require moderate to deep sedation following randomization, for example due to new or evolving medical complication. Whenever the RASS is below (-1), CAM-ICU will not be measured, and will be charted as undetermined. Therefore, only days in which the patient will be CAM-ICU positive, will be counted towards the primary outcome. CAM-ICU positive days prior to randomization will not be counted towards the primary outcome.

[figure not shown]
The secondary outcomes will include the following:

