1. Assess the safety, tolerability, and ease of use of the EyeControl device. This will be achieved by daily review of advance events, and ask patients, families and clinical team regarding challenges of use.
2. Measure the length and intensity of use; We will measure time to first activation, as detailed under the primary goal of the first step, and on a daily basis we will collect data from the device including the number of hours a day the device was worn, how many times it was used for communication, and the type of communication (eg use of predefined sentences, call for help, using new sentences by dictation, entertainment listening etc).
3. Correlate between the monitoring data and clinical data, specifically validate CAM-ICU with nursing and/or study team independent assessment; and correlating wakefulness time with ICU interventions; We will collect from the device on a daily basis the times when the patient has his or hers eyes open, as a marker of wakefulness. We will also record interventions related to sleep and wake cycles, such as administration of

Melatonin or Melatonin agonists, night time antipsychotics, benzodiazepines etc. We will also perform a correlation between the device independent assessment of CAM-ICU, and the clinical team assessment.

- Measure the cognitive and functional long-term outcomes, by phone questioners, to be done in a blinded fashion at 6 months from ICU discharge. This will include a pre-defined battery of tests, as detailed under the Long-Term Outcomes (LTO) Battery section below.

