### Step 2:

Primary Outcome: The time spent alive and non-delirious in the ICU

Covariates/Confounders: age, gender, race, baseline education level, unit to which the patient was admitted to, need for tracheostomy, severity of illness by SOFA or APACHE score on admission and randomization day, categorical reason for admission (e.g. sepsis, ARDS, elective surgery, stroke etc), diagnosis of delirium prior to randomization and the presence of an acute central neurological injury.

Unadjusted Analyses: The time spent alive and non-delirious in the ICU will be evaluated using the stratified variant of the Mann-Whitney U test. In this analysis, patients will be stratified by ICU setting. For other variables, the unadjusted comparison will depend on the type of variable. In general, continuous variables will be compared using a Mann-Whitney U test and categorical variables will be compared using the  $\chi^2$  test.

Adjusted Analyses: The time spent alive and non-delirious in the ICU will be evaluated using a multi-level/mixed-effects quantile regression (median/50th percentile) while controlling for the previously listed covariates. The multi-level/mixed-effects model will be used to account for clustering within ICU setting. In the event that the regression fails to estimate properly, the covariates will be used to generate propensity scores and patients will be stratified into  $\geq 5$  propensity score strata. The time spent alive and non-delirious in the ICU will then be analyzed using the stratified variant of the Mann-Whitney U test. Analyses of the secondary outcomes will depend on the type of variable. Continuous variables will be analyzed using multi-level/mixed-effects quantile regressions (median/50th percentile), binary variable will be analyzed using multi-level/mixed-effects binary logistic regressions, ordinal scales will be analyzed using multi-level/mixed-effects ordinal (cumulative logit) logistic regressions.

Missing Data: In the event of substantial missing data, data will be imputed using a multiple imputation procedure. The type of procedure (e.g. fully conditional specification, hot decks etc.) and the number of imputed data sets will be determined by the amount of missing data and the pattern of missingness.

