## SAFETY MONITORING PLAN

No Data and Safety Monitoring Board is necessary for this prospective trial. No untoward medical occurrence is expected due to subjects' participation in this research. Adverse events In the event subjects report medical illness during follow-up phone calls they will be advised to seek medical evaluation (i.e., emergency department, primary care, etc). During the course of this study, if the principal investigator and/or research personnel believe there are unseen clinically relevant adverse events [related to wearing Eye Control Device], all events will be reviewed by the PI with the clinical team and relevant information reported to the local IRB as unanticipated problems. If an immediate safety concern is discovered by the clinical team, this will be addressed immediately by the study PI and may require no further wearing of the headset.

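### Step 2's first secondary goal counts only device-related adverse events, which controls cannot have, so these data give no randomised comparison; the design section states the same outcome without that limit

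*Combined protocol and SAP*

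**What the plan says.** Determining the safety of the device is part of the stated purpose (Synopsis; Study Purpose). Three places say how safety will be handled in Step 2.

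- **Study Purpose, Step 2, secondary goal 1:** "Specifically, we will assess on a daily basis for any adverse events related to the device".
- **Study Design and Methods, Step 2, secondary outcome 1**, on the same outcome: "This will be achieved by daily review of advance events, and ask patients, families and clinical team regarding challenges of use". The word before *events* is apparently a slip for *adverse*. No restriction to device-related events is stated, and no arm is named.
- **Safety Monitoring Plan:** review by the principal investigator and reporting to the IRB are triggered if staff "believe there are unseen clinically relevant adverse events [related to wearing Eye Control Device], all events will be reviewed by the PI". The same section says "No Data and Safety Monitoring Board is necessary for this prospective trial" and "No untoward medical occurrence is expected due to subjects' participation in this research".

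The comparison is open-label: "Patients will be randomized to use EyeControl for as much as they wish, versus the standard of care". The SAP names no adverse-event analysis. Its general rule for variables other than the primary outcome is that "continuous variables will be compared using a Mann-Whitney U test and categorical variables will be compared using the" chi-square test, and it models secondary outcomes by variable type. Neither the Schedule of Events nor the Subject Hospital Data list has an adverse-event entry.

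**The concern.** An event can be related to the device only in someone who wears it. If the Study Purpose wording governs, the control count is zero by definition, and the safety result is the number of events that unblinded staff chose to attribute to the headset.

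Attribution is a weak instrument here. Agitation, tube removal, skin injury and eye irritation can all occur in ventilated patients without a device, so a moderate excess in the device arm could be put down to the illness. Step 2 could then report few or no device-related events while one of these was more frequent in the device arm. Step 1 cannot settle the question, because it has no control group and is purely descriptive. Step 2 is the only part of the study where background events can be separated from a device effect, and the randomised control arm needed for that already exists.

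**Working it through.** **1. What each statement yields.**

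| Place | Events covered | Arm covered | Randomised contrast? |
|---|---|---|---|
| Study Purpose, Step 2, goal 1 | Device-related only | Device arm by construction | No |
| Study Design, Step 2, outcome 1 | No stated limit | Not stated | Only if controls are reviewed in the same way |
| Safety Monitoring Plan | Believed related to wearing the device | Device arm by construction | Not its purpose (review and reporting rule) |
| SAP, Step 2 | Adverse events not named | Generic between-arm tests | Only if both arms have data |

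No section defines an adverse event, gives an attribution rule, or says how events are found in controls.

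**2. Arm size.** The Sample Size section gives 248 (124 per arm) from a 2-day difference, SD 5.2, alpha 0.05 and 80% power, with the minimal asymptotic relative efficiency of the Mann-Whitney test. I assume a two-sided test and the standard value 0.864 for that efficiency, which the document does not print.

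- Two-sample t-test: 107.09 per arm. 107.09 / 0.864 = 123.94, so 124 per arm and 248 in total. The stated figure reproduces.
- The Synopsis gives 244 (122 per arm). The results below then change by at most 0.2 percentage points.

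**3. What a one-arm count can say.** With 0 attributed events in 124 device patients, the one-sided 95% upper bound is 1 − 0.05^(1/124) = 2.4%. This bounds the rate of *attributed* events. It says nothing about excess events that staff ascribed to illness.

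**4. What two-arm recording would give.** The documents state no adverse-event rate, so the control rates p are assumptions, shown as a range.

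- Half-width of the 95% CI for the risk difference at equal rates: 1.96 × √(2p(1−p)/124). At p = 0.10: 1.96 × √(0.18/124) = 0.075.
- The last column is the device-arm rate that gives 80% power at two-sided 0.05.

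| Assumed control rate | CI half-width (points) | Device-arm rate for 80% power |
|---|---|---|
| 5% | 5.4 | 15.8% |
| 10% | 7.5 | 23.2% |
| 20% | 10.0 | 35.9% |
| 50% | 12.4 | 67.4% |

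**5. Illustration: a doubling from 10% to 20% (assumed).**

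- Extra patients with an event: 124 × (0.20 − 0.10) = 12.4, about 12.
- Power: [0.10 − 1.96 × √(2 × 0.15 × 0.85/124)] / √((0.09 + 0.16)/124) = 0.25 on the normal scale, so about 60%.

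**The case against.** The strongest reply is that the trial does measure harm without attribution. Survival and delirium enter the primary outcome, which is compared between randomised arms. Cognition, function, depression, PTSD and quality of life are assessed at 6 months, blinded. This stands. A reader might infer that Step 2 cannot show whether the device causes harm at all, and the documents do not support that. These outcomes do not, however, directly record unplanned extubation, facial or ocular injury, or agitation, which are plausible harms of a head-worn device.

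Second, the Step 2 design text has no device-related limit. This also stands. A reader might infer that the plan excludes controls from adverse-event review throughout. In fact it is inconsistent in one place and silent on controls in another. The phrase about challenges of use is a separate item in that sentence and does not prove a restriction.

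Third, the SAP's general tests could be applied to a binary safety variable, so it is too strong to say that no between-arm method exists. The gap is upstream: those tests need events found in the same way in both arms.

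Fourth, the Safety Monitoring Plan repeats the relatedness condition, and a reader might treat it as part of the endpoint definition. It governs investigator review and IRB reporting of unanticipated problems. Removing relatedness there could make events of any cause in ventilated ICU patients reportable.

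Finally, the Eye-Control Device section describes an external, easily removed device with no significant side effect according to the manufacturer. That supports a short event list. It does not replace a comparison in a study whose purpose includes safety.

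**Conclusion.** The point holds for the adverse-event data as the Study Purpose section specifies them: a one-arm, open-label attribution count with no randomised contrast. It also holds that this section and the Step 2 design text conflict, and that no section provides for ascertainment in controls or names an arm-level adverse-event comparison.

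The loss is one of information that the trial could provide at little cost. Two-arm recording would not make Step 2 a powered safety trial: 80% power would need roughly 10% versus 23%, and an assumed doubling from 10% would be missed about 40% of the time. It would, however, give an estimate of excess risk with an interval. These figures rest on the assumed control rates and on 124 per arm.

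A reader might also infer that the plan is biased towards a finding of safety by a known amount. The documents give neither event rates nor attribution rates, so the size of any such bias cannot be stated. The expectation of no untoward occurrence does not by itself show that attribution will be suppressed.

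**What to change.** 1. Reconcile Step 2 secondary goal 1 (Study Purpose) with Step 2 secondary outcome 1 (Study Design). Both should say that a short prespecified list of events is recorded identically in both arms, from randomization to ICU discharge, regardless of judged cause. Unplanned extubation, new facial or ocular injury and new agitation are candidates.
2. Record judged relatedness to the device as a separate field, so that the device-related listing is still available as a supplement.
3. Add to the SAP, Step 2: for each listed event, the count and proportion per arm, with the risk difference and 95% CI.
4. Leave the reporting rule in the Safety Monitoring Plan unchanged.

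The cost is protocol wording, one eCRF page and some chart abstraction in the control arm. Charting, vitals and medications are already on the Subject Hospital Data list, which is not limited to one arm. Two limits remain. Ascertainment stays unblinded, and staff may look more closely at the face and eyes of patients wearing the headset, so events already charted routinely in both arms are preferable. Precision is modest, so the results should be read as estimates with intervals and not as tests of safety.

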## SYNOPSIS

Title	Wearable eye-tracking device as means of communication in the critically ill, and mechanically ventilated patient
Short Title	Eye-Control Trial
Principal Investigator	[name], PhD Assistant Professor, Department of Neurology and Neurosurgery, Division of Neurocritical Care Emory University School of Medicine
Study Description	The study will have two steps: (1) safety and efficacy phase, in which we will enroll up to 60 patients, with main goal to experience the use of the device in critical care settings, and better prepare for the second part (burn-in period); (2) a randomized controlled trial that will treat eligible and consented patients with either EyeControl or the current standard of care from a communication stand point. On a daily basis, all patients admitted will be screened according to the predefined inclusion/exclusion criteria. Eligible patients (or their LARs) will be approached by the study team to obtain consent. Once enrolled, and randomized to the intervention arm, the patients will be instructed how to use the EyeControl device and will keep the device on for as long as they would like. While on, the device will collect data as a potential monitor, such as time of wakefulness, and will screen for delirium by CAM-ICU questionnaire. At six months, we will contact the patient to assess his functional and cognitive performance using standardized questioners. Following this interview, the patient will end the participation in the trial.
Purpose	To determine the safety, tolerability, and ease of use of the EyeControl device and determine impact on communication and delirium in critically ill, ventilated patients in the intensive care unit.
Design	This is a single-center, Phase 1/2, two-step prospective, open-label, blinded-endpoint (PROBE) study evaluating the tolerability and efficacy of the EyeControl device.
Objectives	To evaluate the efficacy of a wearable communication device in preventing and treating ICU-delirium in critically ill patients who are admitted to the intensive care unit (ICU) and mechanically ventilated. The study will assess the safety, tolerability, and ease of use of the EyeControl device; examine its potential monitoring capabilities; determine the change in level of frustration and discomfort following use of the device; and measure long-term outcome of these critically ill patients.

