- b. Wakefulness monitoring—the device will record the times in which the patient is awake by monitoring when the patient's eyes are open. This data will later be correlated with outcome measures such as delirium, LOS, and functional outcome. Changes in wakefulness time will also be correlated with ICU interventions such as adding a melatonin-agonist to promote sleep.
- c. CAM-ICU validation—every shift, after the nurse and/or study team member assesses CAM-ICU, the device will repeat the test by using multiple-choice questions and ask the patient to choose the correct answers by blinking. We will later correlate the device's results with the nursing/study team ones.
- d. Reorientation – at a defined time interval, if the patient's eyes will be open, the device will read the patient the current date/time/location.
- e. Entertainment – patients will have the option to listen to music.
- f. Family communication – Families will be supplied with a patient-unique link to record audio messages which the patient will be able to listen to through the device.

To address the secondary goal of proficiency with device operation, we will administer a daily orientation questionnaire via the device. If a patient fails this proficiency check, study staff will perform a device re-training module. The frequency and amount of necessary re-training will be captured as another data parameter.

During the study, we will collect clinical information from the patient's chart including: demographics, diagnoses, use of sedatives or medications that could change cognitive function, nursing charting (including neurological assessment), laboratory results, days on the ventilator, procedures, discharge destination, mortality, and functional outcome. All of these will be taken into account for the final analysis of the study. For example, this data could help us better identify which patients used the device more than others and which could benefit from its monitoring properties apart from its communication function.

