## SAMPLE SIZE

From our retrospective analysis (described in the introduction), we expect about 130 patients per month for the initial screening (ventilated for at least two days). The same patient could be ineligible on a certain day, but become eligible later in the admission (e.g., due to the severity of the illness, the patient is deeply sedated for the first few days, and later sedation is weaned). This will allow us to recruit more patients, at different time points of their admission. Even with this in mind, it would be reasonable to assume that about half of these initially screened patients will not be eligible at any point of their admission due to any one of the exclusion criteria. Of those who will be eligible, we expect a high rate of consent, due to the low risk and the potential benefit of using the device while in the ICU. We therefore expect a rate of about 30 patients a month to be enrolled.

For the first step, we will plan to enroll up to 60 patients, and at least a third of the sample will be from the neuroscience ICU, and specifically patients with an acute brain injury

Given that there are no prior data, there is no clear criteria that would justify a specific number. We believe that having 40 to 60 patients work with this new device would be sufficient to draw initial conclusions about its use and specific indications according to the study aims as stated above.

For the second part of the trial, power calculations are based on previously published BRAIN-ICU trial. In that observational trial patients had  $6.8 \pm 5.2$  delirium/coma-free days within the first 14 days of admission, with an overall rate of about 50% rate of delirium. For the present trial, we considered a 2 day reduction in the time spent delirious as clinically significant. Given these parameters, the present trial will require 248 patients ( $N = 124$  per arm) to achieve sufficient power (80%,  $\alpha = .05$ ) to detect a 2 day difference. In general, a sample size of 248 will provide sufficient power to detect a standardized mean difference of 0.38 (assuming minimal asymptotic relative efficiency of Mann-Whitney U test), an odds ratio of 2.14 for binary variables (assuming maximal variance for a binomial distribution), and a Cohen's  $f$  of 0.18.

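### The Step 2 primary-outcome count starts at an event that only the device arm has, and the CAM-ICU that feeds it is not named, so window and ascertainment can differ by arm

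*Combined protocol and SAP*

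**What the plan says.** **Start and end of counting.** The Step 2 part of Study Design and Methods states: "Delirium will be defined as CAM-ICU positive, starting at day 1 of use (following the day of training"). It closes the window at 14 days from randomization or at ICU discharge, whichever is first; the Synopsis adds extubation. The same Step 2 paragraph leaves out positive days before randomization.

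**What is counted.** That paragraph counts CAM-ICU positive days. The Step 2 primary goal and the Statistical Analysis Plan instead name time alive and free of delirium.

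**Who tests, and when.** The Schedule of Events lists CAM-ICU every 12 hours, with no split by arm. The Synopsis says that the device, while worn, "will screen for delirium by CAM-ICU questionnaire". Step 2 secondary goal 3 adds that "the device will assess CAM-ICU independently, and a study team member will repeat this analysis". The Step 1 text gives a sequence for each shift: "after the nurse and/or study team member assesses CAM-ICU, the device will repeat the test". The Step 2 secondary outcomes treat the device result as something to be validated against the nurse or study-team result.

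**What is not said.** The Step 2 definition names no assessor. It gives no rule for conflicting results on one day, does not exclude device results, and gives no start day for controls or for patients who never operate the device.

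**The concern.** A comparison of day counts needs the same clock in both arms. Here the clock starts at a post-randomization event that one arm cannot have. Whoever builds the dataset will have to invent a control start, and whatever is chosen, the device arm's start still depends on how long training takes. The end is fixed relative to randomization, so a later start gives a shorter window.

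The omission may also be informative. The Synopsis plans to compare patients who could operate the device with those who could not, so failures are expected. Difficulty in learning the device may itself reflect delirium. Leaving these patients without a start day invites their exclusion after randomization.

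The unnamed CAM-ICU source is a second opening. Device results exist in one arm only. If they entered the count, the device arm would have more chances of a positive day.

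**Working it through.** **1. The plan's own sample size.** Inputs from Sample Size: difference 2 days ("we considered a 2 day reduction in the time spent delirious as clinically significant"), SD 5.2, 80% power, alpha 0.05, and the Mann-Whitney efficiency stated as "assuming minimal asymptotic relative efficiency of Mann-Whitney U test", that is 0.864. Two-sided testing is assumed.

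- Normal approximation: 2 × (1.960 + 0.842)² × 5.2² / 2² = 106.1 per arm; divided by 0.864 this is 122.8, so 123.
- Noncentral t: 107.09 / 0.864 = 123.94, so 124 per arm and 248 in total.

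This matches "the present trial will require 248 patients". The number does not depend on the start rule or the CAM-ICU source, so settling either leaves it unchanged on the plan's inputs.

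**2. Who has a start day.**

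| Group | Start under the Step 2 text | End |
|---|---|---|
| Device, trained | day after training | 14 days from randomization, or ICU discharge |
| Device, never operates it | none defined | same |
| Control | none defined | same |

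**3. How much one day is worth.** The documents do not give the delay from randomization to first use. For scale, the cited cohort had 6.8 delirium/coma-free days in 14. If days are spread evenly (an assumption), one day of window holds 6.8 / 14 = 0.49 free days and at most 7.2 / 14 = 0.51 delirious days; the 7.2 also includes coma.

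- Counting positive days: starting one day later lowers the device arm's count by up to about 0.5, in its favour.
- Counting delirium-free days: the same delay lowers its count by about 0.5, against it.

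**4. Effect on type I error.** The standard error of the difference is 5.2 × √(2 / (124 × 0.864)) = 0.710. For a shift b with no treatment effect, two-sided type I error is 1 − Φ(1.96 − b/0.710) + Φ(−1.96 − b/0.710).

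| Shift b (assumed, days) | b / 0.710 | Type I error |
|---|---|---|
| 0.25 | 0.35 | 6.4% |
| 0.5 | 0.70 | 10.8% |
| 1 | 1.41 | 29.1% |

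**5. Extra tests, a conditional illustration only.** Assume that any positive test makes a positive day, errors are independent, sensitivity is 0.9, and the false-positive rate is 2% per test. Controls have 2 tests a day. The device arm has 4 (12-hourly plus device each shift) or 6 (plus a separate study-team repeat). The chance of a false-positive day is 1 − 0.98^k: 4.0%, 7.8% and 11.4% for k = 2, 4 and 6.

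- Controls: observed free days 6.8 × 0.9604 + 7.2 × 0.01 = 6.60.
- Device arm with no effect: 6.8 × 0.9224 + 7.2 × 0.0001 = 6.27 with 4 tests, and 6.02 with 6. The bias is −0.33 or −0.58 days.
- Device arm with a true 2-day benefit: the observed benefit is 1.51 or 1.19 days, with power 57% or 39%, against 76% if both arms had 2 tests.
- If only the common 12-hourly tests count, k is 2 in both arms and the bias from extra tests is zero.

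**The case against.** The strongest reply is that differing ascertainment is inferred. A reader might conclude that device patients receive, and are scored on, extra CAM-ICU tests that controls lack. The documents do not support that:

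- The 12-hourly schedule applies to everyone.
- The device test appears under secondary validation, and a test being validated against the bedside result is unlikely also to be the endpoint.
- The study-team repeat may simply be the routine assessment, since the assessor is described as nurse and/or study team. Nothing says that controls go without it.
- The per-shift device frequency is Step 1 text. Step 2 is called similar only in screening and enrolment.
- No any-positive rule is stated.

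The size of that effect is also fragile. Null simulations (124 per arm, 7 assessable days, any-positive rule, 4 to 6 tests against 2, half of patients ever delirious, perfect sensitivity, independent errors) give type I error of about 19–43% at an assumed 98% specificity and 50–93% at 95%. If false positives cluster within patients (assumed intraclass correlation 0.3), this falls to about 5–8% and 9–21%. Such figures are a conditional worst case.

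On the start day, the Eye-Control Device section reports that nearly all patients learn the device within minutes. If every device patient were trained on the day of randomization and controls were counted from the next day, the windows would coincide. The plan promises neither, and it expects some patients not to succeed.

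The objection removes any claim that ascertainment is stated to differ. It does not touch the start rule.

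**Conclusion.** The concern holds in two parts of unequal strength.

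**Start day: a wrong rule.** Followed as written, it gives the device arm a window set by training, and leaves controls and non-operators with none. This rests on the text alone. Its size is not known, because the documents give no delay; the 6% to 29% type I error above depends on assumed shifts of 0.25 to 1 day and an unchanged SD of 5.2. The direction is not settled either: a later start favours the device if positive days are counted and works against it if delirium-free days are counted.

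**CAM-ICU source: a gap.** Device results that only one arm can have are neither named nor excluded, so ascertainment could differ. Under an any-positive rule, extra tests would count against the device. The two biases cannot be assumed to cancel.

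This should be corrected before Step 2 data are analysed. It does not show that the trial will be biased.

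**What to change.** In the Step 2 outcome definition, and by reference in the Statistical Analysis Plan:

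1. Start counting on the calendar day after randomization in both arms, for every randomized patient, whether or not the device is ever used.
2. Derive the primary outcome only from the scheduled 12-hourly bedside CAM-ICU, with one written day rule for both arms. Calling a day delirious if either scheduled test is positive is one workable choice.
3. Use device results, and any extra study-team repeats, only for the validation goal.

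The cost is a few sentences. No assessments are added, and the sample size stays at 248 on the plan's inputs. The downside is that device-arm days before first use are counted. The device cannot act on those days, so they may slightly dilute the effect. That is the price of a common clock for all randomized patients.
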